## 4. STUDY DESIGN

### 4.1. Overall Design

This is a Phase 2a, single-blind, randomized, placebo-controlled, parallel-group, multiple-dose study to assess the PK, PD, and safety of brensocatib 10, 25, and 40 mg QD in participants with CF. Following review of safety and PK data by the SRC and provided that the SRC deems it appropriate to administer the next higher dose, an additional cohort of participants will receive brensocatib 65 mg QD on the same schedule as the previous cohorts. A tablet formulation of brensocatib 65 mg is not yet available; therefore, participants randomly assigned to the 65 mg dose cohort will receive the following:

- 1 tablet of brensocatib 25 mg QD plus 1 tablet of brensocatib 40 mg QD × 28 days
- OR
- 2 tablets of matching placebo QD × 28 days

[Section 6.3](#) describes the procedures for blinding the study drug.

Overall, the study will enroll approximately 25 to 34 participants. The first three brensocatib dose cohorts (10 mg, 25 mg, and 40 mg QD) will enroll approximately 7 participants each, and the placebo cohort will enroll approximately 4 participants.

For many patients with CF, CFTR modulators are the cornerstone of their treatment ([van der Meer et al., 2021](#)). The proportion of patients prescribed a CFTR modulator has expanded over time, with approximately only 14% of the eligible population not prescribed a CFTR modulator ([CF Foundation Registry, 2020](#)). For the active treatment dose cohorts, there will be 2 strata: approximately 5 participants who have previously received and will continue to receive CFTR modulators as concomitant medication (CFTR modulator stratum), and approximately 2 participants who have either never previously received CFTR modulators or have not been administered CFTR modulators within 30 days prior to Screening (visit 1) and will not receive CFTR modulators during the study (non-modulator stratum). For the placebo cohort, approximately 3 participants will be randomized into the CFTR modulator stratum and 1 participant in the non-modulator stratum.

As described in [Table 1](#), each cohort will enroll participants in a 5:1 ratio (active : placebo) for the CFTR modulator stratum. For the non-modulator stratum, approximately 6 participants will be randomized to receive active treatment (10 mg, 25 mg, and 40 mg brensocatib) and approximately 1 participant to placebo.

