4. STUDY DESIGN

4.1. Summary of Study Design

This is a Phase 2a, single-blind, randomized, placebo-controlled, parallel-group, multiple-dose study to assess the PK, PD, and safety of brensocatib 10, 25, and 40 mg QD in participants with CF. Following review of PK and safety data by a SRC, and provided that the SRC deems it appropriate to administer the next dose, a cohort of participants will receive brensocatib 65 mg QD on the same schedule as the previous cohorts. A tablet formulation of brensocatib 65 mg is not yet available; therefore, participants assigned to the 65 mg dose cohort will receive 1 tablet of brensocatib 25 mg and 1 tablet of brensocatib 40 mg.

Overall, the study will enroll approximately 25 to 34 participants. The first three brensocatib arms (10 mg, 25 mg, and 40 mg QD) will enroll approximately 7 participants each, and the placebo arm will enroll approximately 4 participants. For the active treatment arms, there will be 2 strata: 5 participants who have previously received and will continue to receive CFTR modulators as concomitant medication (CFTR modulator stratum), and approximately 2 participants who have either never previously received CFTR modulators or have not been administered CFTR modulators within 30 days prior to Screening (Visit 1) and will not receive CFTR modulators during the study (non-modulator stratum). For the placebo arm, approximately 3 participants will be randomized into the CFTR modulator stratum and 1 participant in the non-modulator stratum.

Each dose group will enroll participants in a 5:1 ratio (active : placebo) for the CFTR modulator stratum. For the non-modulator stratum, approximately 6 participants will be randomized to receive active treatment (10 mg, 25 mg, or 40 mg brensocatib) and approximately 1 participant to placebo.

If there are no safety issues observed in the first 3 dose cohorts, a 65 mg dose cohort will be similarly randomized: 7 participants (5 participants CFTR modulator and 2 participants non-modulator stratum) in active treatment and 2 participants in placebo (1 participant each in the CFTR modulator and non-modulator strata), increasing the sample size from approximately 25 to 34 participants.

The overview below illustrates the prospective number of participants based on approximately 25 participants in the first 3 cohorts (10 mg, 25 mg, and 40 mg) and approximately 9 participants in the fourth cohort (65 mg).

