4.3. Randomization

After meeting all inclusion criteria and none of the exclusion criteria, participants in each stratum (CFTR modulator and non-modulator) will be randomized by an interactive web

response system (IWRS) in a 1:1:1 ratio to 1 of the first 3 dose cohorts (brensocatib 10, 25, or 40 mg); each cohort, will enroll participants in a 5:1 ratio (active : placebo) for the CFTR modulator stratum. For the non-modulator stratum, approximately 6 participants will be randomized to active treatment in the first 3 cohorts and 1 participant will be assigned placebo. If there are no safety issues in these cohorts, a 65 mg dose cohort will be similarly randomized: 7 participants (5 participants CFTR modulator and 2 participants non-modulator stratum) in active treatment and 2 participants in placebo (1 participant each in the CFTR modulator and non-modulator strata), raising the total sample size from approximately 25 to 34 participants.

This is a single-blind study: participants are blinded to the IP to which they are randomly assigned, as are the study center staff and the Investigator. The site will contact the IWRS prior to the start of IP administration for each participant. The site will record the assigned IP label number on the applicable eCRF, if the participant receives randomized treatment. Unblinding is only to occur in the case of participant emergencies and at the conclusion of the study.

Selected individuals not involved in the conduct of the study may have access to unblinded data as needed for safety review or other data review. These individuals comprise the SRC members and the Independent Clinical Pharmacologist (refer to CSP section 10.1.8).

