7. GENERAL STATISTICAL CONSIDERATIONS

7.1. General

Tables and figures will be provided by treatment group/dose level (10 mg, 25 mg, 40 mg, and 65 mg [if conducted] QD brensocatic, pooled placebo except for PK output). If sample sizes permit, summaries will be further stratified by CFTR modulator and non-modulator.

Treatment arm/dose levels will be presented in this stratified analysis if the number of observations is ≥ 2 . If the assignment to a stratum differs between the randomization file and the eCRF, the randomization file will prevail. In the listings, CFTR modulator use will be indicated by + for participants on CFTR modulator and by - for the non-modulator stratum following the Subject Identifier. For tables in the demographic and safety sections, also a Total column will be presented.

Descriptive statistics for continuous variables will be calculated at scheduled visits (nominal timepoints for PK) and will include the number of participants in the treatment group/dose level of the respective analysis set (N in column header of the table), the number of non-missing- observations (n), the number of observations below limit of quantification (BLQ) for PK and PD tests, arithmetic mean, standard deviation (SD), median, minimum, and maximum. For brensocatic plasma concentrations, the GM with 95% CI and gCV%, for PK parameters (except for t_{\max} and t_{last}), and PD tests, the GM and gCV% will be reported in addition. The GM will be derived by calculating the arithmetic mean of the natural log-transformed observations and then back-transforming the mean by exponentiation. The gCV% will be calculated as: $100 \times \sqrt{\exp[\text{variance of the log-transformed values}] - 1}$. GM and gCV% will only be calculated for quantifiable values above 0. For t_{\max} and t_{last} , only n, median, minimum, and maximum will be presented. For PK parameters, no descriptive statistics will be calculated when fewer than three individual PK parameter values are available. Summaries of continuous variables other than plasma concentrations that have some values recorded using approximate values (e.g., $<$ or $>$) will use the numeric part of the value in calculations. Rules for plasma concentrations BLQ or missing are given in [Section 11](#).

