7.2. Analysis Methods for Estimands

This is a Phase 2a study. No formal hypothesis will be tested and there will not be a confirmatory treatment comparison.

The following ICEs have been identified for this study (see [Section 3](#)):

1. Early discontinuation from the randomized IP for any reason,
2. Not on stable CFTR modulators for participants on modulators,
3. Use of antibiotics during an acute event that could affect NSP levels.

The table below gives an overview which analysis set(s) and strategy to deal with related ICEs will be used for the Estimands.

Estimand	Analysis Set	Strategy for ICEs
Primary, Secondary, and Exploratory PK	PK Analysis Set	For the first ICE, While-on-Treatment strategy: data collected prior to the occurrence of the ICE, i.e., to discontinuation of IP, will be included in the analysis. For the second and third ICE, the Treatment Policy strategy will be used, i.e., all data will be included in the analysis.
Safety	Safety Analysis Set	For the first ICE, While-on-Treatment strategy: data collected prior to the occurrence of the ICE, i.e., to discontinuation of IP, will be included in the analysis. For the second and third ICE, the Treatment Policy strategy will be used, i.e., all data will be included in the analysis.
Exploratory PD	PD Analysis Set	For the first and the third ICE, While-on-Treatment strategy: data collected prior to the occurrence of the ICE, i.e., to discontinuation of IP or to the use of antibiotics with impact on NSP levels, will be included in the analysis.

		For the second ICE, the Treatment Policy strategy will be used, i.e., all data will be included in the analysis.
Exploratory Efficacy, Microbiology	ITT Analysis Set	For the first ICE, While-on-Treatment strategy: data collected prior to the occurrence of the ICE, i.e., to discontinuation of IP, will be included in the analysis. For the second and third ICE, the Treatment Policy strategy will be used, i.e., all data will be included in the analysis.

The While-on-Treatment strategy will be applied for the first ICE: data collected after discontinuation of IP will be excluded from the derivation of PK parameters and from statistical analysis for PK, safety, PD, and efficacy analysis.

The Treatment Policy strategy will be applied for the second ICE: data will be included in derivation of PK parameters and in the PK analysis irrespective of changes in CFTR modulator use.

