If dose proportionality applies, data within stratum (CFTR modulator and non-modulator) will be pooled across dose levels. The log-transformed dose-adjusted C_{max} , AUC_{0-24} , and AUC_{last} for Day 1 and Day 28 will be used as dependent variable in an analysis of variance with the CFTR stratum as independent variable. The LS mean for the difference between strata with 90% CI will be estimated from the model. The estimate and lower and upper confidence limits will be back transformed by exponentiation. The back-transformed difference between the strata is the GM ratio of the strata.

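### SAP 7.1 lets the randomization-file stratum override the eCRF even in SAP 11.1.3, where CFTR modulator use is itself the contrast being estimated

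*SAP*

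**What the plan says.** SAP 7.1 sets one rule for stratum conflicts in all stratified output: "If the assignment to a stratum differs between the randomization file and the eCRF, the randomization file will prevail". The stratum in that file is the one under which the participant was randomised (SAP 4.3).

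The strata are defined by co-medication. The modulator stratum has taken CFTR modulators and continues them. The non-modulator stratum has never taken them, or its members "have not been administered CFTR modulators within 30 days prior to Screening (Visit 1) and will not receive CFTR modulators during the study" (SAP 4.1; Protocol 4.1 agrees).

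SAP 11.1.3 uses the stratum in two ways:
- The dose-proportionality plots show both groups. Visible separation between them may lead to a stratum covariate or to separate analyses.
- If dose proportionality applies, dose-adjusted Cmax, AUC0-24 and AUClast are pooled across doses and analysed by ANOVA with stratum as the only independent variable. "The back-transformed difference between the strata is the GM ratio of the strata", reported with a 90% CI.

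Protocol 9.4.1 plans this exposure comparison. No analysis by verified modulator status is specified. SAP 11.1.1 says concentrations are summarised by use of modulator, which hints at actual use but does not set 7.1 aside.

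**The concern.** Keeping the randomised stratum is an ordinary convention when the stratum adjusts a comparison between randomised treatments. In 11.1.3 nothing randomised is being compared. Modulator use is a patient characteristic, and the question is whether exposure differs with it. Where the eCRF shows that the randomization-file entry is wrong, the SAP would analyse that participant under a co-medication status known to be false, and no benefit of randomisation is protected in return.

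The SAP takes the opposite line on treatment: the PK estimands and the safety and PD analyses use treatment actually received.

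The pooled ratio matters because little else in the PK output gives a quantitative contrast by modulator use. SAP 7.1 gives no descriptive statistics for PK parameters with fewer than three values, and about 2 non-modulators are planned per dose. A mislabelled point could also blur the plots that decide whether the secondary dose-dependency model takes stratum into account.

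**Working it through.** **The plan's own stratum-level precision.** SAP Table 3 (N=5 per stratum and dose) follows from factor = exp(t(0.975, N−1) × s / √N), with s = √ln(1+CV²). At gCV 30%, s = 0.2936 and t(0.975, 4) = 2.776, so the factor is exp(2.776 × 0.2936 / 2.236) = 1.440, as stated. At 40% and 50% it gives 1.613 and 1.798, also as stated. The same s is used below.

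**Inputs.**
- Modulator stratum on active treatment, first three doses: 3 × 5 = 15 (SAP Table 1).
- Non-modulator stratum on active treatment, first three doses: "For the non-modulator stratum, approximately 6 participants will be randomized to active treatment in the first 3 cohorts" (SAP 4.3).
- With the 65 mg cohort: 20 and 8.
- True ratio and number of misfilings: not in the documents, so both are assumed.

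**Effect of misfiling.** Let d be the true log ratio (non-modulator over modulator). Let a be the number of modulator users filed as non-modulator and b the number of non-users filed as modulator, with as-filed stratum sizes n_non and n_mod. Relative to true modulator users, the filed non-modulator mean is (1 − a/n_non)·d and the filed modulator mean is (b/n_mod)·d. The expected as-filed log ratio is therefore

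d × (1 − a/n_non − b/n_mod).

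For 15 versus 6:

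| Misfiling | Share of log ratio kept | True 0.80 appears as | True 1.50 appears as | True 2.00 appears as |
|---|---|---|---|---|
| One modulator user filed as non-modulator | 1 − 1/6 = 83.3% | 0.83 | 1.40 | 1.78 |
| One non-user filed as modulator | 1 − 1/15 = 93.3% | 0.81 | 1.46 | 1.91 |
| One each way | 76.7% | 0.84 | 1.36 | 1.70 |
| Two modulator users filed as non-modulator | 66.7% | 0.86 | 1.31 | 1.59 |

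For 20 versus 8, the shares in the same order are 87.5%, 95.0%, 82.5% and 75.0%. With no discrepancy the share is 100%.

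**Set against sampling error.** The 90% CI factor for the ratio is exp(t(0.95, n_mod+n_non−2) × s × √(1/n_mod + 1/n_non)). For 15 versus 6, t(0.95, 19) = 1.729 and √(1/15 + 1/6) = 0.483, which gives 1.28, 1.38 and 1.48 at gCV 30, 40 and 50%. For 20 versus 8 it gives 1.23, 1.32 and 1.40. One modulator user misfiled among 6 distorts a true ratio of 1.50 by a factor of 1.50^(1/6) = 1.07, and a true 2.00 by 2.00^(1/6) = 1.12. Both lie inside the CI factor.

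**Whether another provision corrects it.** SAP 6.5 allows case-by-case exclusion for protocol deviations. SAP 7.2 provides a Blind Data Review Meeting (BDRM) before database lock. SAP 7.1 marks modulator status in listings, and SAP 8.3 tabulates type of modulator. These can exclude or display a participant, but none moves one to the stratum whose definition is met. Exclusion would cost one of about 6 active non-modulators.

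**The case against.** The strongest reply is that this is a contingent refinement of a descriptive analysis. No objective in Protocol 3 concerns the strata, no hypothesis is tested, and SAP 7.3 says no inferential conclusions will be drawn. The rule is prespecified and conventional. Plausible effects may also be small: Protocol 2.1 reports that potent CYP3A4 and Pgp inhibitors changed brensocatib AUC by 14 to 32%, and Protocol 6.8 calls such interactions unlikely. At an AUC ratio of 1.32, one error among 6 gives 1.32^(5/6) = 1.26, well within sampling error. All of this stands, and it limits the impact. It does not justify keeping a label known to be wrong in an analysis whose only factor is that label.

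A reader might infer more than the documents support:

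- **That one error is half of a dose cell, turning 1.50 into exp(0.5 × ln 1.50) = 1.22.** By-dose PK summaries at the planned 2 non-modulators are not produced: SAP 7.1 requires three PK parameter values, and SAP 11.1.1 three quantifiable concentrations. Half a cell is possible only in small descriptive tables such as AE counts.
- **That nothing enforces the on-study condition.** Inclusion criterion 2b requires a stable regimen, SAP 8.2 monitors and lists deviations, and the BDRM reviews them. The second intercurrent event, "Not on stable CFTR modulators for participants on modulators", does not name a non-modulator participant who starts one. Treatment Policy would keep such data anyway, so that gap concerns flagging and labelling.
- **That the rule distorts the MTD decision.** SAP 5.1 notes that the MTD may differ by modulator use, but SAP 2 leaves the analyses for the Safety Review Committee to its Charter. Nothing shows that the 7.1 rule governs them.
- **That Day 28 PK should be grouped by Day 28 status.** A participant who stops a modulator mid-study would be called non-modulator without meeting that definition, and could sit in different strata on Day 1 and Day 28.

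**Conclusion.** The point holds as a should-fix of moderate weight. SAP 7.1 applies the randomization-file stratum to an analysis in which stratum is the quantity of interest, and no other provision reassigns a misfiled participant. The bias is towards 1 in expectation. For 15 versus 6, one error leaves 83% or 93% of the log ratio, depending on its direction.

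This rests on assumed numbers of misfilings and assumed true ratios. It matters for the ratio only if a discrepancy occurs and dose proportionality is judged to apply. A claim that one error would hide a real difference goes too far, because the 90% CI is wider than that bias at moderate ratios. The case for changing the rule is that the bias is directional, avoidable and cheap to remove.

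**What to change.** In SAP 7.1, limit the randomization-file rule to the efficacy models (the spirometry ANCOVA and the CFQ-R repeated-measures model). For the 11.1.3 stratum comparison and plots, and for the stratified PK, PD and safety summaries, classify participants by eCRF-verified baseline CFTR modulator status against the protocol's stratum definitions. Settle and document each classification at the BDRM, before unblinding.

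List every discrepancy between the randomization file and the eCRF, and report the as-randomised 11.1.3 result as a sensitivity analysis. List and flag on-study modulator changes in either stratum, but do not reclassify anyone by Day 28 status. Align the modulator wording in SAP 11.1.1 with the revised rule.

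The cost is SAP text and one derived variable from data already collected. The downside is that cell counts may differ slightly from the randomised allocation.

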If there are no safety issues observed in the first 3 dose cohorts, a 65 mg dose cohort will be similarly randomized: 7 participants (5 participants CFTR modulator and 2 participants non-modulator stratum) in active treatment and 2 participants in placebo (1 participant each in the CFTR modulator and non-modulator strata), increasing the sample size from approximately 25 to 34 participants.

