**Table 5: 95% CIs for Values of Inter-Participant CV(%) of the AUC0-24 and Cmax GM in Each Actively Treated Cohort**

N	Geometric CV(%)	Geometric Mean 95% CI LL	Geometric Mean 95% CI UL
10	30	GM÷1.234	GM×1.234
	40	GM÷1.317	GM×1.317
	50	GM÷1.402	GM×1.402
7	30	GM÷1.312	GM×1.312
	40	GM÷1.428	GM×1.428
	50	GM÷1.548	GM×1.548

Note: Assumes N=number of participants treated with brensocatib per dose group.

CV = percent coefficient of variation, CI = confidence interval, GM = geometric mean, LL = lower limit, UL = upper limit.

**Table 6: 95% CIs for Values of Inter-Participant CV(%) of the AUC0-24 and Cmax GM for Each Stratum Within Each Actively Treated Cohort**

Geometric CV(%)	Geometric Mean 95% CI LL	Geometric Mean 95% CI UL
30	GM÷1.440	GM×1.440
40	GM÷1.613	GM×1.613
50	GM÷1.798	GM×1.798

Note: Assumes N=5 (number of participants treated with brensocatib per stratum in each dose group).

CV = percent coefficient of variation, CI = confidence interval, GM = geometric mean, LL = lower limit, UL = upper limit.

The range of values for GM CV(%) is based on the results of Day 29 AUClast and Cmax in a study of patients with NCFBE (INS1007-201) and on the results of Day 28 AUC0-24 and Cmax in a multiple-dose study of healthy volunteers (D6190C00001).

For the primary evaluation of safety, N=10 or 7 participants per brensocatib dose group provides 80% or 68% probability, respectively, to detect an AE that occurs with an incidence rate of 15%, and 90% or 80% probability, respectively, to detect an AE that occurs with an incidence rate of 21%.

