#### **9.4.5. Safety Analysis**

All safety analyses will be performed on the Safety Population.

All safety data will be summarized by treatment received (which may differ from the randomized treatment arm) and for the entire safety population, using descriptive statistics.

Participant disposition will be listed and summarized including the number of withdrawals and the primary reason for withdrawal. Participants excluded from any analysis sets will be listed including the reasons for exclusions.

All safety data will be listed for each participant and summarized appropriately. Adverse events will be coded using MedDRA and summarized by SOC and PT. Additional summaries by severity (NCI CTCAE) and relationship to study treatment will be presented.

All clinical safety laboratory data and vital signs will be listed and summarized including changes from Baseline. Any out-of-range laboratory measurements will be flagged in the listings.

The analysis of the safety endpoints and their reporting will be described in more detail in the SAP.

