3. STUDY OBJECTIVES AND ESTIMANDS

3.1. Primary Objectives and Estimands: Pharmacokinetics and Safety

Pharmacokinetic Objective(s)	
To evaluate the pharmacokinetics (PK) of brensocatic in participants with cystic fibrosis (CF) following once daily (QD) oral administration of study drug	
Population	Participants with CF defined by the inclusion and exclusion criteria of the CSP who received brensocatic
Treatment Regimen	1 tablet QD of brensocatic (actual treatment)
Endpoints	C_{max} , t_{max} , AUC_{0-24} , and $t_{1/2}$ on Day 1 and Day 28
Population Level Summary	Mean brensocatic dose levels for C_{max} , AUC_{0-24} , and $t_{1/2}$, median for t_{max}
Intercurrent Event (ICE)	
 Early discontinuation from brensocatic for any reason Not on stable cystic fibrosis transmembrane conductance regulator (CFTR) modulators for participants on modulators
Strategy	
For the first ICE, the While-On-Treatment strategy (including up to Day 35 follow-up period) will be applied.
 
For the second ICE, the Treatment Policy strategy will be used.

C_{max} = maximum plasma concentration, t_{max} = time to maximum plasma concentration, AUC_{0-24} = area under the concentration-time curve from time 0 to 24 hours post-dose, $t_{1/2}$ = elimination half-life.

Safety Objective(s)	
To evaluate the safety of brensocatic compared to placebo in participants with CF	
Population	Participants with CF defined by the inclusion and exclusion criteria of the CSP
Treatment Regimen	1 tablet QD of brensocatic or placebo (actual treatment)
Endpoints	Participant reported treatment-emergent adverse event (TEAE) and type of TEAE
Population Level Summary	Number and percentage of participants with each type of TEAEs and number of TEAEs
ICE	
 Early discontinuation from randomized investigational product (IP) for any reason
Strategy	The While-On-Treatment strategy (including the 28-days follow-up) will be applied.

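### The primary safety objective is brensocatib compared with placebo, but the planned TEAE and AESI tables never pool brensocatib, contrast it with placebo or give an interval

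*SAP*

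**What the plan says.** SAP 3.1 states the safety objective in comparative terms: "To evaluate the safety of brensocatic compared to placebo in participants with CF". Protocol 3 lists the same objective as primary, and SAP 10.2 calls TEAE incidence the second primary endpoint.

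The population-level summary in SAP 3.1 is "Number and percentage of participants with each type of TEAEs and number of TEAEs". SAP 10.2 repeats this for the TEAE tables, and SAP 10.2.1 describes how each AESI category will be summarized. Neither section mentions a difference, a ratio or an interval.

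The columns come from SAP 7.1: "Tables and figures will be provided by treatment group/dose level (10 mg, 25 mg, 40 mg, and 65 mg [if conducted] QD brensocatic, pooled placebo", with a further split by CFTR stratum if numbers permit. The same section adds "For tables in the demographic and safety sections, also a Total column will be presented". The SAP does not define Total. Protocol 9.4.5 says "All safety data will be summarized by treatment received (which may differ from the randomized treatment arm) and for the entire safety population", and the Safety Analysis Set (SAP 6.4) is everyone randomized and dosed, placebo included. Protocol 9.4.5.1 pools placebo across cohorts. No section pools brensocatib for safety.

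On precision, Protocol 9.2 says "For the primary evaluation of safety, N=10 or 7 participants per brensocatib dose group provides 80% or 68% probability" of detecting an AE with 15% incidence. SAP 4.2 repeats the figures.

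**The concern.** Only one planned column combines doses, and it also contains placebo. It therefore estimates neither the rate on brensocatib nor the contrast with placebo that the objective names. A bare 0/7 or 0% in a dose column also gives the reader no sense of the true rate that could lie behind it.

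The AESIs in Protocol 8.2.7 (hyperkeratosis, periodontal or gingival events, infection) are chosen as events related to DPP1 inhibition. A first look at such events in CF would naturally use everyone exposed to the drug as well as each dose.

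The plan's descriptive character does not explain the gap, because lower-ranked endpoints get more. SAP 9.1 gives spirometry LS mean differences from placebo with 95% CIs, and SAP 9.2 does the same for CFQ-R if data allow. SAP 11.1.3 gives 90% CIs for the dose-proportionality slopes and the stratum ratios. Pooling across doses is already foreseen for PK within stratum (Protocol 9.4.1, SAP 11.1.3) and for PD within stratum (Protocol 9.4.4).

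**Working it through.** **Inputs.** Planned numbers are 7 per dose and 4 placebo in the first three cohorts, so 21 active and 25 in all. The 65 mg cohort would add 7 active and 2 placebo, giving 28 active, 6 placebo and 34 in all (Protocol 4.1, SAP 4.2). The incidence rates of 15% and 21% are those in Protocol 9.2.

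**1. The plan's own figures.** P(at least one event) = 1 - (1 - p)^n.
- p = 15%: 1 - 0.85^10 = 80.3%; 1 - 0.85^7 = 67.9%. Stated: 80% and 68%.
- p = 21%: 1 - 0.79^10 = 90.5%; 1 - 0.79^7 = 80.8%. Stated: 90% and 80%.

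All four reproduce. With about 7 per arm planned, the second figure of each pair applies.

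**2. What a zero count leaves open.** The one-sided 95% upper limit is 1 - 0.05^(1/n). The two-sided exact (Clopper-Pearson) upper limit is 1 - 0.025^(1/n).

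| Group | Zero count | One-sided 95% | Two-sided exact |
|---|---|---|---|
| One dose | 0/7 | 34.8% | 41.0% |
| All brensocatib, three doses | 0/21 | 13.3% | 16.1% |
| All brensocatib, four doses | 0/28 | 10.1% | 12.3% |
| Placebo, first three cohorts | 0/4 | 52.7% | 60.2% |
| Placebo, with 65 mg cohort | 0/6 | 39.3% | 45.9% |

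**3. What Total shows.** Assume for illustration 15% on drug and 0% on placebo. Total is expected to read 15% × 21/25 = 12.6%, or 15% × 28/34 = 12.4%. Neither is the active rate or a contrast.

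**4. What the contrast can show.** When both groups have no events, the Newcombe 95% interval for active minus placebo runs from minus the Wilson upper limit for placebo to plus the Wilson upper limit for active. The Wilson upper limit for 0/n is z²/(n + z²), with z² = 3.84.
- 0/7 versus 0/4: -3.84/7.84 = -49% to 3.84/10.84 = +35%.
- 0/21 versus 0/4: -49% to 3.84/24.84 = +15.5%, about +16%.
- 0/28 versus 0/6: -3.84/9.84 = -39% to 3.84/31.84 = +12%.

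Pooling brensocatib tightens the harm side of the interval. The other side is fixed by the placebo count.

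**5. How far pooling helps a side-by-side comparison.** This is the probability, summed over all binomial outcomes, that the observed active percentage is no higher than the placebo percentage. The true rates are assumptions.

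| Active / placebo rate | 7 vs 4 | 21 vs 4 |
|---|---|---|
| 15% / 0% | 32% | 3.3% |
| 15% / 5% | 40% | 20% |
| 15% / 10% | 47% | 34% |
| 25% / 15% | 34% | 32% |

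The tenfold gain in the first row depends on a placebo rate of zero. With a background rate the gain is modest or almost nil.

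**The case against.** The strongest reply is that nothing is lost. Pooled placebo stands next to each dose, so the objective is answered descriptively. The arms do not overlap, so All brensocatib equals Total minus placebo, and all AEs are listed. Both documents disclaim hypothesis testing, SAP 7.3 says no inferential conclusions will be drawn, and the 68% detection probability is stated openly. Much of this stands: a reader can recover the pooled count by subtraction. What the tables do not supply is the interval around it, or any contrast.

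A second reply is that the assumptions favour pooling. Protocol 4.3 reports a possible dose dependency for events that may reflect DPP1 inhibition. If a 15% event occurred only at 40 mg, the chance of seeing none among the 21 would still be 0.85^7 = 32%. Protocol 2.3.3 reports that infections were similar across treatment groups in earlier trials, so a zero placebo rate is unrealistic for them. Both points are right. They are reasons to keep the dose columns and to make no claim of a large gain for the comparison.

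Third, 4 to 6 placebo participants limit the contrast under any layout. That is true, and the interval would make the limit visible.

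A reader might go further and infer that a safety conclusion, or the 65 mg decision, rests on seeing no event in 7 people. The documents do not support this. The condition is worded "If there are no safety issues observed in the first 3 dose cohorts", which covers about 21 exposed participants. Protocol 4.1.5 and SAP 5.1 make the decision an SRC judgement on unblinded data from all cohorts, and no section treats a zero count in an arm as proof of safety. What the SRC will be shown is set in its charter and table shells, which were not available here.

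**Conclusion.** The point holds as a gap in reporting. A primary endpoint with a comparative objective gets counts and percentages by dose, pooled placebo and a mixed Total, with no pooled brensocatib group, no contrast and no interval.

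The firm gain is in bounding the rate on brensocatib. With zero events, the one-sided 95% limit falls from 35% in one arm to 13% over three doses or 10% over four (two-sided exact: 41%, 16% and 12%). Read as a limit for every dose, the pooled figure assumes similar risk across doses. Otherwise it bounds only the average over the doses given. The numbers also assume that planned enrolment is met.

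The gain for the comparison is smaller and depends on the placebo rate. It would be too strong to say that a pooled column rescues the comparison, that DPP1-related events are expected equally at every dose, or that the planned tables prevent any comparison with placebo.

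**What to change.** In SAP 7.1, 10.2 and 10.2.1:
- Keep the per-dose and pooled placebo columns. Add an All brensocatib column (10, 25 and 40 mg, plus 65 mg if run) to the TEAE and AESI tables, next to Total or in its place. If Total stays, define it as active plus placebo.
- For overall TEAE incidence and for each AESI, give exact 95% CIs for each arm and for All brensocatib.
- Give the risk difference, All brensocatib minus pooled placebo, with its 95% CI. Name the interval method and label the contrast as descriptive.
- Report a zero count with its upper limit, and state whether the limit is one-sided or two-sided.

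The cost is SAP and table-shell wording and routine programming before database lock. Enrolment, visits, doses and the SRC process are untouched. There are two downsides. Pooling can mask a dose trend, which is why the per-dose columns stay. The contrast will look uninformative with 4 to 6 placebo participants, and the text should say so.
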